Protocol Title

Multi-center, 6-month, randomized, and controlled trial to compare the effects of Myo Munchee therapy and Oral Motor Therapy (OMT) in pediatric patients (aged 3-5 years) to treat maxillary deficiency and orofacial myofunctional dysfunction (OMD).

General Information

Protocol Title			
Multi-center, 6-month, randomized, controlled trial to compare the effects of Myo Munchee therapy and Oral Motor Therapy (OMT) in pediatric patients (aged 3-5 years) to treat maxillary deficiency and orofacial myofunctional dysfunction (OMD).			
Protocol identifying number	0001		
Version Number	27	Version date	25/04/2025
Clinical Trial Sponsor			
Sponsor Name	Myo Munchee		
Sponsor Contact			
Telephone			
Email	[contact]		
Address	[name]		
Principal Investigator			
Name			
Telephone			
Email	[contact]		
Personnel authorized to sign the protocol and the protocol amendment(s) for the Sponsor (ICH GCP 6.1.3)			
Name			
Telephone			
Email	[contact]		
Address	[name]		
Independent Review Board			

Name	Allendale Investigational Review Board
Status of ethical review	 Approved  In progress  To be submitted
Trial Sites	1. [name] 2. [name]
Funding for the Clinical Trial	
Funding Body Name	Myo Munchee (Operations) Pty Ltd

Safety and Monitoring Contacts

Clinical Trials Involving Investigational Medical Device	
Study Coordinator and Principal Investigator - remote	
Name	
Telephone	
Email	[contact]
Address	[name]
Study Coordinator - Chicago	
Name	
Email	

Introduction and Hypothesis

In combination, or as a sole disease entity, when Skeletal Malocclusion (SM), Orofacial Myofunctional Dysfunction (OMD), Sleep Disordered Breathing (SDB) and/or Tethered Oral Tissue (TOT) traits are present in Early Childhood (before the age of 72 months old), a young child's quality of life and general health status may be compromised.

Over a period of six months, when SM, OMD, SDB and/or TOT traits are individually, or in some combination, present in early childhood, Oral Motor Therapy (OMT) with, or without, adjunctive intervention with Myo Munchee Therapy (MMT), will result in improved SM, OMD, SDB and/or TOT trait co-morbidities.

Purpose

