Linear mixed model with random subject intercept will be used to compare treatment and control groups. Adjustments for demographic and clinical variables will be performed if necessary. The main statistical analysis will be performed using intention-to-treat (ITT) principle with a secondary per-protocol analysis. For the ITT analysis, all subjects with at least baseline measurements will be included, while for the per-protocol analysis, only subjects who did not deviate from the protocols will be included.

All statistical hypothesis testing will be performed using 5% significance level.

Measurements

Clinical Measurements

Dental Measurements

[Videos](#) demonstrations of measurement taking process.

- **Palatal transverse width** - measured at the primary canines (cusp tips) and the lingual surface of the 2nd molars (narrowest distance measured at gingival margins):
 - a. Anterior intercanine measured between the primary canines (cusp tips) - Image 2a of Thilander et al. 2009.

[figure not shown]

Figure. Image taken from Figure 2a of Thilander et al. 2009

- b. Posterior intermolar measurement between the lingual surface of the 2nd molars (narrowest distance measured at gingival margins): Bogue index

JOUR. A. M. A.
DEC. 2, 1922

the width of the maxillary arch
determines whether or not there is room for normal
nasal breathing.

Figure. Image taken from Bogue, E.A. 'The Relations of the Dental Arches to Pathologic Affections of the Nasopharynx'. Amer Med. Assoc., Transactions of Section on Dis. of Childhood, 58:110 (1907).

- **Palatal sagittal depth/length** - measured anteriorly from the incisive papilla perpendicularly to a line connecting and posteriorly along the same line perpendicular to the disto-gingival margins of the 2nd molars (at alveolar crests);
 - a. Posterior depth/length: Figure 3 from Thilander et al. 2009

[figure not shown]

Figure. Image taken from Figure 3a of Thilander et al. 2009

(b) Arch Depth

[figure not shown]

Figure. Image taken from Figure 3b of Thilander et al. 2009

- **Palatal vault height:** measured from the center of the line connecting the disto-gingival margins of the 2nd molars (at alveolar crests) down to the contact with the mid-palatal suture.

Palatal Height

Figure. Image taken from Figure 4 of Thilander et al. 2009

- Any changes to patients usual oral routines

C-GASP questionnaire

This survey collects clinical information on the signs and symptoms associated with breathing disturbances.

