- Sleep inventory - <https://www.sleepinventory.com/>
- Children's Airway Screening Taskforce

Patient Recruitment

Patient recruitment process

Refer to Appendix for detailed description

Marketing and advertising materials for recruitment

Informational A4 letters for each individual practice have been developed so patients can read and understand what is required to participate in the study. Refer to Appendix for an example.

Financial Information

Compensation to patients for Participation

The compensation associated with participating in the study will be broken into treatment groups.

1. Myo Munchee only group

- a. Free Myo Munchee device
- b. Follow up measurement appointments at T10 and T26: covered by Myo Munchee
- c. Treatment appointments: all 15-minute appointments covered by Myo Munchee
- d. \$250USD voucher if fulfill these criteria:
 - i. Attend all measurement appointments (3 total)
 - ii. Complete all monthly compliance logbooks (6 total)
 - iii. Attend minimum 6 out of 7 of the 15-minute treatment appointments (7 appointments)

2. OMT only group

- a. \$250USD voucher if fulfill these criteria:
 - i. Attend all measurement appointments (3 total)
 - ii. Complete all monthly compliance logbooks (6 total)
 - iii. Attend minimum 6 out of 7 of the 30-minute treatment appointments (7 appointments)

3. Myo Munchee and OMT group

- a. Free Myo Munchee device
- b. \$250USD voucher if fulfill these criteria:
 - i. Attend all measurement appointments (3 total)
 - ii. Complete all monthly compliance logbooks (6 total)
 - iii. Attend minimum 6 out of 7 of the 30-minute treatment appointments (7 appointments)

4. Control group

- a. Free Myo Munchee device at end of study
- b. \$250USD voucher if fulfill these criteria:
 - i. Attend all measurement appointments (3 total)

The \$250 USD voucher that can be spent at one or split across multiple practices

Costs for Participation

The costs associated with participating in the study will be broken into the treatment groups and to the specific appointments below:

1. Myo Munchee only group

- a. Measurement appointments:
 - i. Initial appointment: billed to patient's insurance provider as an initial evaluation consultation

2. OMT only group

- a. Initial and follow up measurement appointments: billed to patient's insurance provider as an initial evaluation consultation

- b. All treatment appointments: billed to patient's insurance provider as OMT has established therapeutic benefit

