3. Myo Munchee and OMT group
 - a. Initial and follow up measurement appointments: billed to patient's insurance provider as an initial evaluation consultation
 - b. All treatment appointments: billed to patient's insurance provider as OMT and Myo Munchee has established therapeutic benefit
4. Control group
 - a. No cost

Ethics

- To be submitted to Allendale Investigational Review Board - <https://www.allendaleirb.com/>
- Email: [contact]
- <https://www.wma.net/policies-post/wma-declaration-of-helsinki-ethical-principles-for-medical-research-involving-human-subjects>

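### Treatment and follow-up measurement visits are sponsor-paid in the Myo Munchee only group but billed to insurance in both OMT groups, so payment is randomised together with treatment

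*Protocol*

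**What the plan says.** The payment terms are in the protocol under Financial Information, split between Compensation to patients for Participation and Costs for Participation.

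- **Group A (Myo Munchee only).** Under Compensation: "Treatment appointments: all 15-minute appointments covered by Myo Munchee" and "Follow up measurement appointments at T10 and T26: covered by Myo Munchee". Under Costs, only the initial measurement appointment is billed to the insurer.
- **Group B (OMT only).** Under Costs, item a: "Initial and follow up measurement appointments: billed to patient's insurance provider as an initial evaluation consultation". Item b: "All treatment appointments: billed to patient's insurance provider as OMT has established therapeutic benefit".
- **Group C (Myo Munchee and OMT).** Item a has the same wording as for Group B. Item b: "All treatment appointments: billed to patient's insurance provider as OMT and Myo Munchee has established therapeutic benefit".
- **Group D (control).** No cost.

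Every group can earn the same $250 voucher. In A, B and C it depends on all three measurement visits, six compliance logbooks and attendance at treatment visits, which for B and C reads "Attend minimum 6 out of 7 of the 30-minute treatment appointments (7 appointments)". In control it depends on the measurement visits alone.

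The trial's funder is "Myo Munchee (Operations) Pty Ltd". On analysis, the Data Analysis section says: "The main statistical analysis will be performed using intention-to-treat (ITT) principle with a secondary per-protocol analysis".

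**The concern.** Allocation decides both the treatment and who pays for it. A family randomised to B or C may face a co-payment, a deductible or a refused claim for its allocated treatment and its outcome visits. A Group A family does not face this after the initial visit. No inclusion, exclusion or screening criterion asks for insurance or confirmed OMT cover, and the protocol text shown does not say who pays what an insurer does not.

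Two things are at stake.

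- **Delivered treatment.** The clinician chooses OMT exercises child by child, and families are taught at the treatment visits. Missed visits can therefore lower what an OMT child receives. Under intention-to-treat these children stay in their arm and dilute its effect. A per-protocol analysis drops them and leaves a group selected partly on ability to pay. Neither analysis separates price from treatment.
- **Outcome data.** The palatal measurements are the primary outcomes and are repeated at T10 and T26. Those visits are billed in B and C and free in A and D, so missing data could differ by arm for a reason unrelated to efficacy.

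**Working it through.** **1. Who pays, by arm**

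| | A | B | C | D |
|---|---|---|---|---|
| Initial measurement | insurer | insurer | insurer | no cost |
| T10 and T26 measurement | sponsor | insurer | insurer | no cost |
| Treatment visits | sponsor | insurer | insurer | none |

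**2. Direction, if cost reduces attendance in B and C**

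- A versus B: B is lowered, so the contrast moves towards the device.
- B versus D: diluted.
- A versus C and C versus D: C is lowered. C contains the device, so these contrasts move against a device-containing arm.
- B versus C: both are billed, so no difference in payment rule.

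**3. The protocol's own power figures.** Inputs from Power Calculation: 12 per group and d = 1.2. The 5% level is from Data Analysis. I took the test as a two-sided two-sample t-test, since sidedness is not stated.

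- 12 v 12, d = 1.2: 80.2% (stated: at least 80%).
- 6 v 12, d = 1.2: 61.6% (stated: 60%).
- d = 0.6, 80% power: 44.6, so 45 per group (stated: 45).

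The figures reproduce, so the same test is used below.

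**4. Illustration.** Assumptions, none from the protocol: A and B are truly equal at d = 1.2 against control; k of the 12 Group B children lose a fraction f of the effect because of cost; the SD is unchanged.

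Spurious gap between A and B = 1.2 × (k/12) × f. Effect of B against D = 1.2 − gap.

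| k | f | Gap (SD) | B–D effect | B–D power | A–B rejection at nominal 5% |
|---|---|---|---|---|---|
| 0 | – | 0 | 1.20 | 80% | 5% |
| 1 | 1 | 0.10 | 1.10 | 73% | 5.6% |
| 2 | 0.5 | 0.10 | 1.10 | 73% | 5.6% |
| 3 | 0.5 | 0.15 | 1.05 | 69% | 6.4% |
| 4 | 0.5 | 0.20 | 1.00 | 65% | 7.6% |
| 2 | 1 | 0.20 | 1.00 | 65% | 7.6% |
| 3 | 1 | 0.30 | 0.90 | 56% | 10.8% |
| 4 | 1 | 0.40 | 0.80 | 47% | 15.5% |

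If the extra spread from mixing affected and unaffected children is simulated, the three f = 1 rows with k = 2, 3, 4 give B–D power of about 61%, 50% and 40%, and A–B rejection of about 6%, 9% and 12%.

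**5. Volume of treatment visits in B and C (24 children)**

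- The voucher terms count 7 visits: 24 × 7 = 168 sessions × 0.5 h = 84 h.
- Total Time commitment gives 2 h before and 2 h after T10, which is 8 half-hour visits: 24 × 8 = 192 sessions × 0.5 h = 96 h.
- In Group A the same counts give 12 × 7 = 84 or 12 × 8 = 96 quarter-hour sessions (21 or 24 h), already funded.

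**The case against.** **Out-of-pocket cost is inferred.** The text says that the insurer is billed and gives no co-payment, deductible or refusal rate. Consent pages and the recruitment appendix are not in the text at hand and might contain cost terms. The initial visit is billed to insurance in A, B and C, which suggests that insured families are expected. All of this stands and leaves the size unknown. It does not remove the difference: the protocol protects Group A in writing and lists the B and C billing as a cost of taking part.

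**The voucher rewards attendance.** It does, in the very arms where attendance might fall, and it may soften the effect. But Group A can earn the same $250, so it does not close the gap between arms.

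**Most OMT happens at home.** The protocol plans 39 hours at home against about 4 hours of treatment visits, with videos of all exercises. A child who misses later visits has not lost the whole treatment, so the full-loss rows are the severe end of the range.

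**A versus B is not the powered contrast.** The power calculation concerns treatment against control, and Data Analysis speaks of comparing treatment and control groups. The A–B rejection rates therefore apply to a contrast that the title names but the protocol does not power.

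**A stronger reading.** A reader might infer that the distortion runs one way, in the sponsor's favour. The documents do not support that. Group C uses the device and is billed like Group B, so in A–C and C–D the same mechanism works against a device-containing arm. Only A–B tilts towards the device.

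**Conclusion.** The difference in payment rules is a stated term of the design. It confounds A–B and A–C with price and can dilute B–D and C–D. Because T10 and T26 visits are billed in B and C only, it can also cause uneven loss of primary-outcome data. Intention-to-treat and per-protocol analyses do not remove it.

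The size cannot be derived from the protocol. With 12 per arm, a true effect of 1.2 SD, constant SD, and 2 to 4 Group B children losing half to all of the effect, B–D power falls from 80% to between 73% and 47%, and A–B rejection rises from 5% to about 6% to 16%. If cost changes no family's attendance, there is no bias. A reader should not take the table as a forecast or conclude that OMT families will in fact pay. It shows that, in arms this small, a few affected children can matter. This is a change worth making before enrolment, not a fatal flaw.

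**What to change.** Apply one payment rule to treatment visits in Groups A, B and C, and one to the T10 and T26 measurement visits in all four groups. The cleanest version is that the sponsor covers them.

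At minimum, state that no family in any arm pays out of pocket for study treatment or for T10 and T26 measurement visits, and that the sponsor meets co-payments, deductibles, refused claims and the bills of uninsured children. Revise items a and b for Groups B and C under Costs for Participation accordingly, and add the matching lines to their Compensation lists. Changing item b alone would leave the outcome visits unequal.

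The cost is an amendment and sponsor money, with no added patients, staff or procedures. Full coverage of B and C treatment visits is 168 to 192 half-hour sessions (84 to 96 hours). The T10 and T26 visits come on top: at the 4 hours per child in Total Time commitment, 24 × 4 = 96 hours. The minimum version costs only what insurers do not pay.
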